Our ultimate aim in our proposed study is to reduce overall levels of compulsory admission through an intervention designed to reduce compulsory readmissions and for this to be suitable for and engaging to Black African, Caribbean and British service users due to their overrepresentation in this setting. Our finding in a recent review (17) that past compulsory admission is one of the main risk factors for future compulsory admission provides a rationale for focusing on preventing **repeat** compulsory admission. The proposed pathway is via an individualised crisis planning and monitoring intervention for people who have just had a compulsory admission. Reducing repeat compulsory admissions is one of three main potential pathways to reducing compulsory admissions, the others

being early intervention to prevent the crises that lead to hospitalisation, and diversion to community alternatives at the point of admission.

We suggest that, in order to maximise chances of substantially reducing compulsion, there should be research investment in each. Our plans and chosen strategy for reducing compulsory admissions are rooted in the evidence syntheses that we led to inform the Independent Review of the Mental Health Act in our (SJ and BLE) leadership roles in the NIHR Mental Health Policy Research Unit (MHPRU). We also draw on subsequent consultations, including a large stakeholder event in March 2019: the purpose of this event was for a mixed group, including service users and carers, researchers, clinicians and policy makers, to discuss priority next steps for research to reduce compulsory admission (18). We drew the following conclusions following this work:

- Firstly, our literature syntheses established that there is currently very little evidence on what interventions or service arrangements can reduce compulsory admissions or readmissions (14). Very few trials of psychological, psychosocial or team interventions include compulsory admission as a primary or even secondary outcome. This is unlikely to change imminently: our search of the ISRCTN, ClinicalTrials.gov and EU Clinical Trials Register found no trials in progress with compulsory admission as primary outcome. Thus, there is a long way to go to reach a point where interventions can be rolled out with confidence that they prevent compulsory admission, so that it is very desirable that robust trial evidence is urgently obtained regarding effectiveness and cost-effectiveness of candidate interventions.

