5.1 Inclusion criteria

5.1.1. Service user participants

Eligible participants will (a) have been compulsorily detained under Section 2 or Section 3 of the Mental Health Act during their current hospital admission, (b) be due to receive community mental health care locally post-discharge, (c) be aged 18 and above, and (d) have capacity to consent at the time of recruitment.

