8. TRIAL PROCEDURES

8.1 Pre-intervention assessments

8.1.1. Primary outcome

Number of participants who had been compulsorily detained or not, which will be taken from medical notes.

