8.1.2. Other Clinical Outcomes

Service engagement will be measured through routinely collected data from patient records about all service use during data-collection periods.

The remaining clinical outcome measures will be collected by a research assistant blind to treatment allocation. The measures will be administered during a face to face, or if not possible remote, interview between the participant and the research assistant.

Satisfaction with services will be examined using the Client Satisfaction Questionnaire (CSQ). It is an 8-item scale where participants can rate their satisfaction on a 4-point likert scale.

Personal recovery will be measured by the 15-item Process of Recovery Questionnaire (QPR) (33). Participants can score from 0 (disagree strongly) to 4 (agree strongly) on each item and score a total a maximum of 40 on the scale.

Self-management confidence will be measured using the Mental Health confidence scale (34). Participants rate their mental health confidence on 16-items on a 6-point likert scale from very non-confident to very confident.

Quality of life will be measured by the REQOL-10 and EQ-5D-5L. They are both widely used measures in clinical trials and has been successfully used with psychosis populations. On the REQOL, participants rate their quality of life on 10-items from 0 to 4. A participant can score a total of 40 (36). For the EQ-5D-5L, participants rate quality of life on 5-items (mobility and self-care) where they can score from 1 –3. A participant can score a total of 15.

Psychiatric symptoms will be assessed using the Brief Psychiatric Rating Scale. Participants are rated by a clinician on 18 items from 0 (not assessed) to 7 (extremely severe) to give an overall score of psychiatric symptoms.

Economic costs will also be assessed using an adapted version the “generic UK mental health” version of the Client Service Receipt Inventory (37). The CSRI has also been adapted to examine service use and service engagement.

We will also record demographic and clinical/service user characteristics, including Community Treatment Order status, previous admission history and clinical diagnosis.

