11. STATISTICAL CONSIDERATIONS

11.1 Primary outcome

Compulsory readmission measured at 12-months.

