11.5 Statistical analysis

11.5.1 Clinical outcome analysis

The study will follow best practice guidance for the reporting of pilot RCTs (CONSORT, Schulz, Altman & Moher, 2010; Eldridge et al., 2016). The focus of the analysis will be on key indicators of feasibility, including participant recruitment, retention and acceptability of the intervention, which will be summarised descriptively using frequencies and percentages. Continuous clinical outcome measures will be summarised separately by study arm using means and standard deviations or medians and interquartile ranges, as appropriate for the distribution of the data. Binary outcome measures will be summarised using frequencies and percentages. The quantity of missing data for each clinical outcome will be examined and likewise summarised by study arm. This pilot study will not have sufficient statistical power to assess the effectiveness of the intervention, although it will allow an assessment of whether the direction and magnitude of any effect found for the proposed primary outcome are consistent with a hypothesis that the programme is effective in reducing repeat detentions. For this reason and to test the analysis envisaged for a future, fully powered, effectiveness RCT, clinical outcomes at follow-up time points will be compared between study arms, using linear or logistic regression models as appropriate, and adjusting for the baseline measure of the outcome in question.

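### For compulsory readmission the stated baseline adjustment is empty: eligibility gives every participant the same baseline value, so the primary comparison is in effect unadjusted

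*Protocol*

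**What the plan says.** Section 11.5.1 sets one model rule for the clinical outcomes: they are compared between arms by linear or logistic regression, "adjusting for the baseline measure of the outcome in question". The study summary repeats it, and neither place makes an exception. One reason given for fitting these models is to see whether the "direction and magnitude of any effect found for the proposed primary outcome are consistent with a hypothesis that the programme is effective". The other is to try out the analysis intended for a full-scale trial.

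Section 11.1 gives the primary outcome as "Compulsory readmission measured at 12-months". It is binary, so the logistic model applies. The trial parameters section (printed as 10.5.2) calls compulsory admissions a clinical outcome, which brings it under the rule.

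Section 8.1.1, under pre-intervention assessments, describes the primary outcome measure as "Number of participants who had been compulsorily detained or not, which will be taken from medical notes". Inclusion criterion (a) in section 5.1.1 requires participants to "have been compulsorily detained under Section 2 or Section 3 of the Mental Health Act during their current hospital admission". The summary says primary measures are collected at baseline, but Appendix 1 marks compulsory admission only at 12 and 24 months.

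Section 8.1.2 also records participant characteristics, "including Community Treatment Order status, previous admission history and clinical diagnosis". None of these is named as a covariate.

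**The concern.** Adjusting for the baseline value works for the questionnaire scales, where each participant has a score that varies. It does not carry over to an event outcome in a sample selected because the event has just happened to everyone. A covariate that takes one value for the whole sample adjusts for nothing.

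Two things are at stake. First, the model is there partly as a rehearsal for the definitive trial, and as written it does not exercise covariate adjustment on the outcome proposed as primary there. Second, the protocol's background states that "past compulsory admission is one of the main risk factors for future compulsory admission". With 40 per arm, the arms can differ by chance on that history, and the stated model would not correct for it even though the result would be labelled baseline-adjusted.

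**Working it through.** The protocol derives no figure on this point, so there is none to reproduce. The check has two parts.

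**1. Is the covariate informative?**

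Inputs: 80 participants, 40 per arm (section 11.2); baseline indicator = 1 for everyone (sections 5.1.1 and 8.1.1).

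- Variance of the indicator: 0.
- Design matrix of intercept, arm and baseline indicator: 3 columns, rank 2. The indicator duplicates the intercept, so its own coefficient is not identified.
- Illustrative fit with 17/40 control and 11/40 intervention events, close to the 43% and 28% of the Swiss trial cited in section 2. The deviance is 101.602 with or without the indicator. The arm odds ratio is (11/29)/(17/23) = 0.513 without it and 0.512 with it; the gap is convergence tolerance.

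The arm effect is estimable and unchanged. If Appendix 1 is followed instead, no baseline value exists, and the result is the same: no adjustment.

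**2. How much could uncorrected imbalance matter?**

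The protocol gives no prevalence or risk by admission history, so these are assumptions: 50% of participants with an earlier compulsory admission, and readmission risk 33% with and 16.5% without (ratio 2, mean 24.75%).

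- Standard deviation (SD) of the between-arm imbalance: √(2 × 0.5 × 0.5 / 40) = 0.112, or 11.2 points.
- Shift in the risk difference at one SD: 0.112 × (0.33 − 0.165) = 0.018, or 1.8 points.
- An imbalance of 15 points or more in either direction: probability about 0.18; shift 0.15 × 0.165 = 0.025, or 2.5 points.

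Benchmark: the Swiss two-year rates, halved in time under an assumed constant hazard.

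- Intervention: 1 − √(1 − 0.28) = 15.1%. Control: 1 − √(1 − 0.43) = 24.5%. Difference: about 9.4 points.
- Standard error: √[(0.151 × 0.849 + 0.245 × 0.755) / 40] = 0.0885, or 8.85 points.
- Expected events: 40 × 0.151 + 40 × 0.245 ≈ 16.

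The one-SD shift is 1.8/8.85 = 0.21 of a standard error, and the 15-point case is 2.5/8.85 = 0.28. The covariate would explain 0.25 × 0.165² / (0.2475 × 0.7525) = 3.7% of outcome variance, so adjustment would cut the standard error by 1 − √(1 − 0.037), or under 2%.

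Range: hold the mean risk at 24.75% with 50% prevalence, and vary the risk ratio.

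| Assumed risk ratio | Risks with / without history | Gap | One-SD shift | Share of standard error |
|---|---|---|---|---|
| 1.5 | 29.7% / 19.8% | 9.9 points | 1.1 points | 0.13 |
| 2 | 33% / 16.5% | 16.5 points | 1.8 points | 0.21 |
| 3 | 37.1% / 12.4% | 24.75 points | 2.8 points | 0.31 |

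A prevalence of 30% or 70% lowers the SD of imbalance to √(2 × 0.3 × 0.7 / 40) = 10.2 points, so 50% is the least favourable case.

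**The case against.** The strongest reply is that section 8.1.1 gives no time window. Because the index detention is already an eligibility fact, the baseline measure could mean detention before the index admission. That would vary, and it could come from the admission history in section 8.1.2. A statistical analysis plan, which is not at hand, might define it so. The reading is possible, but the protocol does not state it: admission history is listed as a participant characteristic, apart from the outcome measures. The wording that is there produces a constant, so this reading is the remedy rather than an answer.

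A second reply is that sections 3.2.2 and 4.2 list clinical outcomes separately from compulsory readmission, so the rule may not have been meant for it. Against that, the trial parameters section calls compulsory admissions a clinical outcome, and 11.5.1 cites the primary outcome as a reason for the models.

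A third reply concerns weight, and it stands. The trial is a declared unpowered pilot focused on feasibility, no progression criterion in the protocol uses the adjusted estimate, and the shifts above are small beside the standard error.

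A reader might also infer that the primary analysis cannot be run, or that its result would be biased. The documents do not support either. Only the covariate's own coefficient is unidentified; software will normally drop the term, and the remaining arm comparison is protected by randomisation. Nor do they support calling past compulsory admission the strongest predictor: section 2 puts it among the main risk factors and does not rank it, and nothing shows how well it discriminates among people who have all just been detained.

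**Conclusion.** The point holds as a specification error of moderate weight. On the protocol's own definition and eligibility rule, the stated baseline adjustment for compulsory readmission does nothing, and on Appendix 1 there is no baseline value to adjust for. This conclusion rests on the text alone and needs no assumed figures.

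The consequence is a comparison labelled adjusted that is in fact unadjusted, and a rehearsal that omits covariate adjustment for the proposed primary outcome. The numerical cost in the pilot is modest: about 1.8 points at a one-SD imbalance (1.1 to 2.8 over the range shown), against a standard error of about 8.85 points. Those figures depend on the assumed prevalence, the assumed risks and a constant hazard. They do not make this a must-fix. The reason to correct it is that the correction is cheap and would carry into the definitive trial's primary model. The questionnaire outcomes are not affected.

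**What to change.** In section 11.5.1 and the study summary, state that for compulsory readmission the model adjusts for compulsory admissions before the index admission, either any versus none or a count, over a look-back period fixed in advance. Take it from the previous admission history that section 8.1.2 already records, and confirm that this record captures legal status and dates, which the protocol does not say. Make section 8.1.1 and Appendix 1 agree with this. Keep baseline-score adjustment for the questionnaire scales.

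Stating plainly that this outcome has no baseline adjustment would also remove the contradiction, but it would give up the rehearsal.

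Cost: one sentence in two places, a matching entry in the schedule, and possibly slightly more detailed record extraction. The model gains one real parameter with few events to support it (about 16 on the assumed rates), so a single binary or count term is as much as it should carry.

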10.5.2. Trial parameters

The thresholds for deciding whether recruitment and retention indicate sufficiently good feasibility and acceptability will be finalised during Phase 1, following review by the Independent steering committee. Regarding follow-up on the clinical outcome compulsory admissions, availability of this measure from electronic case records will allow a high follow-up rate to be attained: our goal in the study will be at least 90%. We will decide on a minimum number of sessions at which the intervention will be deemed to have been delivered as intended, likely to be at least 50%, and will assess how many participants reach this.

12. ASSESSMENT AND MANAGEMENT OF RISK

The table below summarise the risks and mitigations of all test above standard care that are being performed in a table:

Intervention	Potential risk	Risk Management
Assessment measure completion Delivery of therapy	There may be a small possibility that the participant will get upset or emotionally distressed whilst taking part in the assessment measures and therapy.	
If participants become distressed whilst completing the outlined assessment tools, the study researcher will use their skills to make sure the participant feels as safe as possible. This will include monitoring the participants' mental state, offering breaks, offering the opportunity to talk through their difficulties (if they want to), providing a safe and containing environment to conduct the research and ensuring a person-centred stance is taken.
 
In the event that the participant becomes distressed and it is not manageable by the/research assistant, the therapist/research assistant will also contact their named nurse/care coordinator if there is concern that they are at a risk to themselves or self-harming intent/suicide is disclosed. The researcher will follow the trusts safe visiting policy.
 
Participants are also free to withdraw at any point.
 
Participants who are deemed high risk by their clinical workers will be seen at the service where additional clinical staff are present

13. RECORDING AND REPORTING OF ADVERSE EVENTS

13.1 Definitions

Term	Definition
Adverse Event (AE)	Any untoward medical occurrence in a patient or trial participant, which does not necessarily have a causal relationship with the intervention involved.
Serious Adverse Event (SAE).	
Any adverse event that:
 
 • results in death, • is life-threatening*, • requires hospitalisation or prolongation of existing hospitalisation**, • results in persistent or significant disability or incapacity, or • consists of a congenital anomaly or birth defect. • Other 'important medical events' may also be considered serious if they jeopardise the participant or require an intervention to prevent one of the above consequences

* A life-threatening event, this refers to an event in which the participant was at risk of death at the time of the event; it does not refer to an event which hypothetically might have caused death if it were more severe.

** Hospitalisation is defined as an in-patient admission, regardless of length of stay. Hospitalisation for pre-existing conditions, including elective procedures do not constitute an SAE.

13.2 Assessments of Adverse Events

Each adverse event (AEs) will be assessed for severity, causality, seriousness and expectedness as described below.

13.2.1 Severity

The generic categories below are given for use as a guide. You may have a more specific scale that you want to use related to the disease (e.g. CTCAE criteria), amend as required.

Category	Definition
Mild	The adverse event does not interfere with the participant's daily routine, and does not require further intervention; it causes slight discomfort
Moderate	The adverse event interferes with some aspects of the participant's routine, or requires further intervention, but is not damaging to health; it causes moderate discomfort
Severe	The adverse event results in alteration, discomfort or disability which is clearly damaging to health

13.2.2 Causality

The assessment of relationship of adverse events to the intervention is a clinical decision based on all available information at the time of the completion of the case report form. The differentiated causality assessments will be captured in the trial specific AE Log and/or SAE form. The following categories will be used to define the causality of the adverse event:

Category	Definition
----------	------------

Related	A causal relationship between the intervention and an adverse event is at least a reasonable possibility, i.e., the relationship cannot be ruled out.
Not related	There is no reasonable possibility of a causal relationship between the intervention and an adverse event.
Not Assessable	Unable to assess on information available.

13.2.3 Expectedness

All SAEs assigned by the Investigator or delegate as suspected to be related to the intervention will be assessed for expectedness as outlined below.

Category	Definition
Expected	An adverse event which is consistent with the information about the intervention
Unexpected	An adverse event which is not consistent with the information about the intervention

** This includes listed events that are more frequently reported or more severe than previously reported.*

No AEs or SAEs are expected as a result of the intervention.

13.2.4 Recording of Adverse Events

14. All adverse events will be recorded in the medical records in the first instance. All Adverse events will be recorded in the Case Report Form (CRF) following consent.

14.1 Procedures for recording and reporting Serious Adverse Events (SAEs)

All serious adverse events will be recorded in the medical records and the CRF, and the sponsor's AE log. The AE log of SAEs will be reported to the sponsor at least once or twice per year. Where the event is unexpected and thought to be related to the intervention, this will be reported by the Investigator to the Health Research Authority within 15 days. Completed SAE forms must be sent within 5 working days of becoming aware of the event to the Sponsor **Email forms to** [contact]

14.2 Managing serious adverse events across research sites

Mental health practitioners delivering the trial intervention, their NHS supervisors, and managers of the participating NHS services will be directed to report any adverse events involving trial participants to the relevant site PI without delay. In addition, the study researcher will contact the mental health practitioner's supervisor and involved NHS service manager at each site at least monthly, to ask them to screen service and patient records for AEs for trial participants. A report of the circumstances of the AE, and the informant's view on causation and severity will be sought from the PI or study researcher, who will then contact the study CI without delay. The study CI ([name]), as the trial's Clinical Reviewer and a Consultant Psychiatrist, will complete an SAE form and make final assessments of severity, causality and expectedness, in discussion with the PI where possible. The CI will then send the completed SAE form to the Sponsor and the site PI, and disseminate any necessary safety information to the other site PI.

SAEs will be followed up and screened for each participant until the participant's 6-month follow-up research interview and active involvement in the study are completed.

SAEs will be reported to the sponsor until the end of the trial. Follow-up SAE forms (clearly marked as follow-up) will be completed and emailed to the JRO if required as further information becomes available.

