7. INTERVENTIONS

7.1 Name and description of intervention under investigation

Crisis psychoeducation intervention: The plan for the intervention is described here but is subject to change following phase 1 of the study.

Each intervention participant will receive:

- (a) Up to four initial sessions with a “personal mental health worker” (a clinical psychologist or equivalently skilled worker - terminology, desirable qualifications and characteristics to be reviewed in Phase 1). These will focus on: initial relationship building; individualised education about risk factors for relapse; information about accessing and using services and treatments; information on their specific mental health problem; identification of individual risk and protective factors; exploration of individual recovery goals. Meetings may be conducted in person, or via video-conference depending on current Covid-restrictions and participants’ preference. The content of the intervention will be finalised by the coproduction group.
- (b) Production, in electronic or paper form, of a crisis plan/advanced statement, outlining warning signs to monitor strengths and resources, a personalised crisis action plan and details of sources of help and support. This will be adapted to incorporate emerging policy guidance on content of Advance Choice Documents regarding preferences for crisis management.
- (c) Monthly telephone or video call monitoring over one year, initiated by the personal mental health worker, including checking warning signs and prompting coping responses.

The trial intervention will be provided as an addition to mental health care of usual type and quality, received by members of this groups.

Treatment as usual: This will be the routine care that participants receive. This includes multi-disciplinary care from mental health nurses, nursing assistants, psychiatrists, pharmacists, occupational therapists and psychologists in both the inpatient and community setting.

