8.3 Intervention Procedures

8.3.1. Crisis psychoeducation intervention

Each participant will receive up to four initial sessions with a “personal mental health worker” to undertake the crisis intervention and develop a crisis plan/advanced statement. They will then

receive monthly telephone or video call monitoring over one year, initiated by the personal mental health worker, including checking warning signs and prompting coping responses.

The four intervention sessions will begin on the acute inpatient ward and if needed continue into the community (either remotely or face to face in a community service setting or at the participants home). The therapists will receive a one-to-two-day training package in order to deliver the intervention, which will be manualised in the course of the initial 8 month intervention development phase. The training will be delivered by a clinical psychologist and an expert by experience. All mental health workers will have access to monthly supervision whilst they are delivering the therapeutic intervention.

All mental health workers will record information on the content and delivery of the sessions, including information on the session length, location and types crisis management strategies utilised (e.g. assessment, formulation, relapse prevention) on a pre-defined database.

All therapy sessions will be audio recorded if the participants gives written consent for them to do so. Fidelity to the intervention will be measured using a fidelity checklist which will be finalised in collaboration with the coproduction panel.

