8.4.3. Secondary outcome measures

All secondary clinical outcomes outlined in section 7.1 will be repeated six months post randomisation and twelve months post randomisation. These will be conducted either face to face or remotely.

Service engagement and service use will be collected from medical records at 12 and 24 months.

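### Section 14.2 gives the intervention arm extra adverse event reporting routes, so any event counts shown by arm are open to ascertainment bias

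*Protocol*

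**What the plan says.** Protocol section 14.2 sets out how adverse events come to the trial's attention. "Mental health practitioners delivering the trial intervention, their NHS supervisors, and managers of the participating NHS services will be directed to report" any such event to the site principal investigator. There is also an active prompt: "the study researcher will contact the mental health practitioner's supervisor and involved NHS service manager at each site at least monthly". The prompt asks its two recipients for a check of the notes, and that request is worded for trial participants generally and is not limited to one arm.

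Section 13.2.4 adds that "All adverse events will be recorded in the medical records in the first instance", followed by the case report form. Section 14.2 ties follow-up and screening of serious events to the 6-month research interview and the end of active involvement.

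The arms differ in contact with trial workers. Under section 8.3.1, "Each participant will receive up to four initial sessions with a “personal mental health worker” to undertake the crisis intervention". Section 7.1 then adds "Monthly telephone or video call monitoring over one year, initiated by the personal mental health worker, including checking warning signs and prompting coping responses". Controls receive routine care alone (sections 3.2.2 and 8.3.2), and no trial worker is attached to them.

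The research interviews at 6 and 12 months are common to both arms, but sections 8.1.2 and 8.4.3 specify no adverse event question and the schedule in Appendix 1 has no adverse event row.

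**The concern.** Two of the three named reporter groups, and one of the two recipients of the monthly prompt, exist because of the intervention. A control participant has no counterpart to either. The personal mental health worker also speaks to the participant every month and asks about signs of deterioration, so events that never reach the notes by another path can surface there. The qualitative interviews in section 8.4.4, which ask about harms, also include service users from the intervention group only.

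What is at stake is how event counts by arm will be read. The protocol expects no adverse events from the intervention (section 13.2.3) and plans no data monitoring committee (section 15.2). The management group reviews serious events (section 15.1), and the study's data inform the decision on a full trial (section 3.2.2). If more events are recorded in the intervention arm, readers could not tell better detection from harm, and a real excess could be put down to detection. If the source of each report is not captured at the time, it cannot be reliably reconstructed later.

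**Working it through.** The protocol gives no adverse event rate and no detection rate, so there is no stated figure to reproduce. The check has three steps.

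**1. Routes by arm**

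| Route | Intervention | Control |
|---|---|---|
| Practitioner delivering the intervention (14.2) | yes | no |
| Practitioner's supervisor as direct reporter (14.2) | yes | none named |
| Monthly prompt to that supervisor (14.2) | yes | not excluded by the wording, but no working link to controls is described |
| Service manager, report and monthly prompt (14.2) | yes | yes |
| Medical records, then case report form (13.2.4) | yes | yes |
| Adverse event question at research interviews (8.1.2, 8.4.3, Appendix 1) | none specified | none specified |

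**2. Planned worker contacts in which an event could surface**

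Inputs: up to 4 sessions (8.3.1), monthly calls for a year, about 12 (7.1), and 40 participants per arm (11.2).

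- Over one year: 4 + 12 = 16 per intervention participant; 40 × 16 = 640 in the arm.
- To the 6-month interview: 4 + 6 = 10 per participant; 40 × 10 = 400 in the arm.
- Control arm: 0 on either count.

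**3. Possible size, with no true difference between arms**

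Let *s* be the share of events caught by routes common to both arms, and *e* the share of the remainder caught by the intervention-only routes. Both are assumptions.

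Apparent ratio = [*s* + (1 − *s*)*e*] / *s*

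| *s* | *e* = 0.25 | *e* = 0.50 | *e* = 0.75 |
|---|---|---|---|
| 1.0 | 1.00 | 1.00 | 1.00 |
| 0.9 | 0.925/0.9 = 1.03 | 0.95/0.9 = 1.06 | 0.975/0.9 = 1.08 |
| 0.7 | 0.775/0.7 = 1.11 | 0.85/0.7 = 1.21 | 0.925/0.7 = 1.32 |
| 0.5 | 0.625/0.5 = 1.25 | 0.75/0.5 = 1.50 | 0.875/0.5 = 1.75 |

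As an example in participants, assume a true risk of 40% in both arms, *s* = 0.7 and *e* = 0.5. Recorded in control: 40 × 0.4 × 0.7 = 11.2. Recorded in intervention: 40 × 0.4 × 0.85 = 13.6. The apparent ratio is 13.6/11.2 = 1.21.

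If both arms have the same routes (*e* = 0, or the extra route applied equally), the ratio is 1.00 at every *s*.

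**The case against.** The strongest reply is that the protocol plans no between-arm safety comparison. Adverse events are not among the feasibility, primary or secondary outcomes (sections 8.4.1 to 8.4.3), and the regression models in section 11.5.1 are for clinical outcomes. Events are handled case by case, and more reporters in the intervention arm serve that purpose well. This stands, and it limits the point to event counts that are displayed by arm.

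A second reply is that controls are not left to the service manager alone. The record screen is worded for all trial participants, the notes are the first place of recording in both arms, and both arms are interviewed about service use. Serious events are chiefly deaths, life-threatening events and admissions (section 13.1), which should reach those records. This also stands, and it is why the effect on such events is probably small. It does not make the routes equal, because a common floor with a supplement in one arm is still unequal. Section 14.2 also covers adverse events generally, including those that may never be noted, and does not define which manager counts as involved for a control participant.

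A third reply is that tabulation belongs in the statistical analysis plan, which is not shown. That is fair for table layout. How events are found, and whether the source is recorded, is trial conduct that section 14.2 itself fixes.

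Finally, sampling error dominates. The 13.6 against 11.2 example has SE(log ratio) = √(1/13.6 − 1/40 + 1/11.2 − 1/40) = 0.336, so an approximate 95% interval of 0.63 to 2.35 around 1.21. Forty per arm could not settle safety even with perfect ascertainment.

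**Conclusion.** The unequal routes are on the page, and by-arm adverse event counts are open to ascertainment bias towards more recorded events in the intervention arm. The size is unknown. It is nil if the common routes catch everything, about 3% to 8% inflation if they catch 90%, and about 11% to 32% if they catch 70%, all on assumed values.

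A reader might infer more than this, in three ways that the protocol does not support:

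- That the safety comparison is shown to be biased by some definite amount. No detection rates are given. Even an assumed 80–90% detection against 60–75% spans ratios from 0.80/0.75 = 1.07 to 0.90/0.60 = 1.50, and nothing in the protocol supports those inputs.
- That the pilot is thereby prevented from answering whether the programme is safe. It sets no such test, and its size would not allow a firm answer in any case.
- That the efficacy results are compromised. Compulsory readmission is taken from the medical notes (section 8.4.2) and is not affected through this route.

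The change is still worth making before data collection, because it is cheap and the source of a report is hard to recover afterwards.

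**What to change.** In section 14.2:

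1. State that the at-least-monthly record screen is applied identically to every participant in both arms, and say who carries it out for control participants.
2. Add a source-of-report field to the adverse event log and case report form, completed when the event is first notified.
3. Base adverse event counts by arm on events found by the common record screen.
4. Show all events in a separate listing by source, including those known only through intervention workers or supervisors. None should be dropped, since workers are best placed to notice harms arising in sessions.

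Immediate reporting by workers stays as it is.

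The cost is one extra field, a second table, and the effort of confirming that the planned screen reaches all 80 participants at the same frequency. The existing extraction does not supply this: "Service engagement and service use will be collected from medical records at 12 and 24 months", which is less frequent than the screen in section 14.2. Because the source of a report can reveal allocation, the field should be handled by the unblinded staff described in section 5.5.

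Some asymmetry can remain. Under section 13.2.4, an event disclosed only to a worker may be entered in the notes and then be found by the record screen. The source field makes such cases visible where the first notification came from the worker, but does not remove them.
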